The enhanced hospital-based surveillance will be in place prior to the introduction of RTS,S/AS01, generating data for Programme Advisory Group review to confirm the integrity of the surveillance and allowing an assessment of the comparability of facilities in implementing and comparison areas in terms of completeness and quality of the data. Data from the enhanced HMIS will be monitored until the end of the evaluation, approximately 50 months after the start of vaccination (see section 9.2.1), using automated data routines to evaluate completeness and internal consistency of records.

Children with any sequelae following a diagnosis of meningitis or cerebral malaria will be invited to re-attend hospital for follow-up appointments after hospital discharge. These will be scheduled at intervals considered appropriate by the attending clinician.

If, at any time, the attending clinician suspects the admission is related to RTS,S/AS01 the procedures to report an AEFI should be followed (see section 13) and the Evaluation Partner's Clinical Surveillance Coordinator notified by phone or SMS text message. The fact that an event was reported as an AEFI will be captured in the CRF.

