Table 1: Number of clusters randomized in each country, number of surveillance hospitals, and the number of clusters within the catchment of the sentinel hospitals

Country	Clusters	Population: annual birth cohort mean (range)	Sentinel Hospitals	Clusters in sentinel hospital catchments	Catchment clusters: annual birth cohort mean (range)
Ghana	66	3975 (912,8954)	8	32	4628 (1202,8954)
Kenya	46	5488 (2702,10739)	6	28	5559 (3487,10739)
Malawi	46	4820 (2816,8112)	4	17	5115 (2816,8112)
TOTAL	158	4661	18	77	5074

(excludes areas where the GSK phase 4 study is being done in each country)

Hospital and mortality surveillance will start when RTS,S/AS01 vaccination begins, or as soon as possible after that date, and be maintained until 46 months from the start of RTS,S/AS01 vaccination.

Administration of doses of RTS,S/AS01 and of other vaccines will be recorded by the EPI programme in each country using their normal record keeping system. Vaccination coverage will also be measured independently through community surveys. A survey will be undertaken at baseline, to measure coverage of EPI vaccines and Vitamin A, deworming treatment, malnutrition by MUAC, and the prevalence of *P.falciparum* infection (using an HRP2 Rapid Diagnostic Test). A second survey will be undertaken after about 18 months to measure coverage of EPI vaccines and, in RTS,S clusters, coverage of 1,2 and 3 doses of RTS,S in children 12-23 months of age. A third survey is planned to measure coverage of the fourth dose of RTS,S.

The MVPE was designed to detect differences in disease and mortality rates, over 46 months, between RTS,S and comparison clusters. Specifically, it was powered to detect a reduction in all-cause mortality in each country in RTS,S clusters of 10% or more (with 90% power) ; to detect a 2.6-fold or greater increase in the rate of meningitis (all countries combined) with 90% power ; to detect an increased incidence of cerebral malaria if the true rate is increased by 1.7-fold or more; and to detect an increase in the female:male mortality ratio with 90% power if the ratio is increased by 1.15-fold or more.

3. Description of the clusters

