This analysis approach takes account of potential imbalance between the implementation and comparator areas. In each country, surveillance for meningitis and severe malaria will be maintained in a subset of clusters, through selected hospitals. Each hospital draws patients primarily from a small number of clusters. These clusters may not be well balanced between intervention and comparator with respect to population size, the underlying risk of meningitis or malaria, access to hospital, and the diagnostic performance of the hospital. For mortality, although a larger number of clusters has been randomized, there is also a risk of imbalance if it is not possible to implement surveillance uniformly well in all clusters. Pre-intervention data on these outcomes is not available as surveillance was established for the purpose of the evaluation, at the same time as the vaccine was introduced.

Methods for estimating rate ratios and rate differences are detailed below.

Assumptions of the analysis approach:

The approach assumes that:

- a) the incidence by age is such that there are expected to be enough cases for analysis (in both group B and group A)
- b) the age of cases will be determined sufficiently accurately to assign them to group A or B reliably
- c) there is limited catch-up vaccination, so that a group can be defined based on age who would not have received RTS,S vaccine

d) for rate ratios, we have assumed that the ratio of person time between Group A and group B is the same in each cluster and in both intervention and comparator areas although this assumption could be relaxed if cluster-specific data were available. The population size of the cluster does not need to be known to estimate rate ratios, but for rate differences, population denominators are needed. For both effect measures an assumption is that the ratio of incidence of the outcome of interest between eligible and non-eligible age groups, would be the same in implementation and comparison areas in the absence of the malaria vaccine. We would expect this to hold for other conditions, this could be checked by comparing incidence ratios of outcomes unrelated to malaria. Such “tracer” conditions could then be used to adjust for an imbalance, by comparing the ratio (eligible:non-eligible) for the outcome of interest to the corresponding ratio for the tracer conditions, and comparing this double ratio between implementation and comparator areas.

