and applied census estimates of the ratio of girls to boys among under 5's in each district in each year, and census estimate of the sex ratio at birth, to obtain estimates of births and population under 5 for boys and girls in each cluster in each year.

[figure not shown]
To estimate the population under 5 years of age, in each calendar month from Jan 2018 to Dec 2023, by month of age, in each MVIP cluster, an iterative method was used, by applying age-specific survival estimates, while preserving the census estimates of total annual births and mid-year totals under 5 years of age. We first estimated the number of births in each calendar month, and the total population under 5 in each calendar month, and then used an iterative procedure consisting of two steps, firstly applying age-specific survival to the population in each month to give the population in the next month, and then re-scaling to maintain the correct total population under 5, these steps being repeated until convergence. Census estimates of the infant and under5 mortality for the appropriate district [6], and the UN IGME estimate of the neonatal mortality rate [7] were used. This procedure gives cluster populations with annual mean under-5 total, and annual births, equal to census estimates, with age structure consistent with the census estimates of infant and child mortality. The estimated population in each month of age for each calendar month were then used to calculate totals for vaccine-eligible and non-eligible children. These were used for calculation rates and rate differences, but were not used in estimation of rate ratios.

Ghana and Kenya: Similar approach will be used for Ghana and Kenya. In Malawi, population estimates, projections, and mortality rates were available by district from the 2018 census. In Ghana, census projections were available from the 2014 census and estimates of mortality rates from the 2014 DHS. In Kenya, provisional population estimates from the 2019 census were available, and estimates of mortality rates were obtained from the 2014 DHS.

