$$\frac{m_0}{(m_0 - 1)T_{0,A}T_{0,B}} \sum_{i=1}^{m_0} (n_{0,i,A}n_{0,i,B} - r_{0,A}n_{0,i,B}T_{0,i,A} - r_{0,B}n_{0,i,A}T_{0,i,B} + r_{0,A}r_{0,B}T_{0,i,A}T_{0,i,B})$$

where m_0 is the number of clusters in the comparator area. The variance of $[r_{1,A} - r_{1,B}]$ is calculated similarly. The variance of the rate difference (comparator-RTS,S) is $V(RD) = V(r_{0,A} - r_{0,B}) + V(r_{1,A} - r_{1,B})$, and the 100(1- α)% confidence interval is $RD \pm t_{\alpha/2, m_0 + m_1 - 2} \sqrt{V(RD)}$. Rate differences will be calculated separately for each country. The rate difference RD is *the number of cases averted (or added) as a result of RTS,S vaccine being introduced into an area, in the age groups of children eligible for the vaccine, expressed per 1000 child years (or other suitable units)*. The estimated values will be specific to the analysis population chosen (A1, eligible for RTS,S; A2 eligible for 3 doses of RTS,S; or A3 eligible for 3 doses and followed up to 39 months of age), and the time point at which analysis is done.

Rates and rate differences will be calculated for mortality and for hospital outcomes. Incidence rates of hospital admission, based on sentinel hospitals, are influenced by access to hospital, and the availability of alternative health facilities. Rate differences are therefore inevitably context-specific and reflect the local situation. Rates and rate differences for hospital outcomes refer to the rates of

admission to the sentinel hospitals from the defined source populations. Rate differences therefore represent a minimum bound on the rate difference that would be observed if there was uniform access to hospital and there were no competing hospitals.

Rate ratios

In practice for rate ratios, the person time will cancel out. It is only the ratio of person time in group A and group B that is relevant (rather than the total person time for the cluster) and as we are unlikely to have cluster-specific data about this ratio, we assume it is the same in each cluster within a country.

After cancelling the person time, the ratio of the total events in group A to group B is $R_1 = n_{1,A}/n_{1,B}$ in the RTS,S area and $R_0 = n_{0,A}/n_{0,B}$ in the comparator area.

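### No common surveillance start date is set, and the rate ratio drops person-time, so a difference between arms in average start date would shift the mortality and severe malaria estimates

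*SAP*

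**What the plan says.** SAP 2 (Design of the evaluation) states that "Hospital and mortality surveillance will start when RTS,S/AS01 vaccination begins, or as soon as possible after that date" and will "be maintained until 46 months from the start of RTS,S/AS01 vaccination". The closing date is fixed, so a late opening is not made up. No section sets a common opening date by country, arm or cluster.

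The primary rate ratio divides events in age-eligible children (group A: A1 for safety, A2 for impact) by events in non-eligible children (group B) within each arm, then compares arms. SAP 6(d) says that "for rate ratios, we have assumed that the ratio of person time between Group A and group B is the same in each cluster". It applies this to the two arms alike, with a caveat: "although this assumption could be relaxed if cluster-specific data were available". SAP 20 (Rate ratios) repeats the assumption: "as we are unlikely to have cluster-specific data about this ratio, we assume it is the same in each cluster within a country". The T_B/T_A term shown in Table 10 is then dropped, leaving R_j = n_jA/n_jB.

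SAP 10 and Annex 1 estimate each cluster's population by month of age and calendar month. Of these estimates the SAP says: "These were used for calculation rates and rate differences, but were not used in estimation of rate ratios".

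The documents differ on when surveillance opens. Protocol 10.3 says "The enhanced hospital-based surveillance will be in place prior to the introduction of RTS,S/AS01". SAP 6 says surveillance was set up at the same time as vaccine introduction. Protocol 6 equates the first dose in country 1 with the start of data capture.

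**The concern.** The within-cluster A/B comparison removes differences between clusters that stay constant over time, such as access to hospital or a steady level of under-reporting. It does not remove a difference in the observation window, because the A:B mix changes steeply with calendar time. At launch nearly every child under 5 is in group B; group A then grows month by month. A cluster that opens late loses mainly B events, so its A:B event ratio rises with no vaccine effect.

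A later average opening in the RTS,S arm would push the rate ratio up and hide benefit. A later opening in the comparator arm would push it down and create apparent benefit. SAP 7 handles the other end of the window (if comparator vaccination starts early, the affected cells are excluded in both arms), but there is no matching rule for the start.

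**Working it through.** **Reproducing the plan's own example.** The SAP Annex 2 event totals are 29 and 15 (A, B) in the RTS,S arm and 21 and 17 in the comparator arm. (29/15)/(21/17) = 1.5651, the stated 1.5650794. The stated 95% CI (0.6136 to 3.9921) and P value (0.336) also reproduce. In that dataset yb/ya is 3.50 in every cluster, so restoring person-time changes nothing (1.5651). The example has the assumption built in and cannot reveal the problem.

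**Person-time model.** Inputs are Malawi's groups in SAP 7. Let t be months from the start of vaccination.
- Group A: born from 1 November 2018, so aged up to t+6 months; from 5 months of age for A1, from 8 months for A2.
- Group B: aged 1-5 months, or born before September 2018 and so aged t+8 months and over, up to 60 months.
- Assumptions: uniform ages, no mortality loss, flat incidence.

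The widths of the age bands at time t are:
- A1: (t+6) − 5 = t+1
- A2: (t+6) − 8 = t−2, from t = 2
- B: 4 + (52−t) = 56−t

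Integrated from 0 to 46:
- A2 = 44²/2 = 968
- A1 = 46²/2 + 46 = 1,104
- B = 56×46 − 46²/2 = 1,518
- A:B = 0.638 (A2) and 0.727 (A1)

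Opening 3 months late removes 168 − 4.5 = 163.5 from B (10.8%), 0.5 from A2 (0.05%) and 7.5 from A1 (0.7%). The A2 ratio becomes 967.5/1,354.5 = 0.714, and 0.714/0.638 = 1.12.

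The table gives the factor by which A:B rises when a whole arm opens L months late:

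| L (months) | A2, month 46 | A1, month 46 | A1, month 24 |
|---|---|---|---|
| 1 | 1.04 | 1.04 | 1.05 |
| 2 | 1.08 | 1.07 | 1.10 |
| 3 | 1.12 | 1.11 | 1.15 |

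**Sensitivity.** With the declining age profile of mortality in Protocol 9.5, and with Ghana's cut-offs, the 3-month A2 factor at month 46 is 1.12-1.13. If only half of one arm's clusters are 3 months late, it is about 1.06. Kenya was not modelled, because SAP 7 gives a non-eligible birth cut-off (January 2019) that conflicts with its eligible cut-off (1 September 2018).

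**Against the effects of interest** (SAP Table 5, after coverage and contamination):
- Mortality 0.93: with the RTS,S arm 2 months later, 0.93 × 1.078 = 1.00; with the comparator arm 2 months later, 0.93/1.078 = 0.86.
- Severe malaria 0.76: a 3-month difference gives 0.76 × 1.12 = 0.85 or 0.76/1.12 = 0.68.
- Meningitis 5.66 and cerebral malaria 2.03: with the comparator arm 3 months late, the month-24 factor gives 5.66/1.155 = 4.90 and 2.03/1.155 = 1.76, both still far from 1.

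**Later gaps.** A gap raises A:B if the A:B ratio in the lost months is below the cumulative 0.638, and lowers it if above. Setting (t−2)/(56−t) = 0.638 gives t of about 23. Losing month 40 (38 units of A2, 16 of B) gives 930/1,502 = 0.619, a fall of about 3%.

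**The case against.** The strongest reply is that the documents give no evidence of an arm-level difference. The SAP's vaccination section gives one start date per country, SAP 6 describes surveillance and vaccine starting together, and Protocol 7.6.5 requires identical monitoring in both arms. A country-wide delay affects both arms and cancels. Clusters were randomised, those containing sentinel hospitals were split equally, and under Protocol 10.2.1 one hospital may serve both arms and so share an opening date. Delays unrelated to arm add noise, not bias. As an assumed illustration, openings spread uniformly over 0-6 months (SD 1.73) with 23 clusters per arm give a standard error of 1.73 × √(2/23) = 0.5 month for the arm difference, about 2% on the ratio, and the SAP's between-cluster variance would reflect that. All of this stands. A reader might infer that clusters or arms did open on different dates; the SAP only leaves room for it.

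Existing safeguards count in part. The tracer-condition double ratio in SAP 6(d) would show a window difference and largely correct it, but it is worded as something that could be done. SAP 13 tabulates weekly reports by month, cluster and arm, but no analysis rule follows from them.

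It might also be said that Annex 1 refutes the SAP's statement that cluster-specific A:B data are unlikely. It does not: in Malawi the age structure comes from district ratios and district mortality applied to cluster totals. The populations can carry a calendar window, which is what is needed here, but they are not observed cluster ratios.

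**Conclusion.** The gap is real but conditional. The plan permits unequal surveillance windows, its rate ratio does not adjust for them, and the A/B comparison does not remove them. A difference of 1, 2 or 3 months between arms in average opening date would shift the A2 ratio at month 46 by about 4%, 8% or 12%, against an expected mortality effect of 7-10%. These figures rest on Malawi's definitions, flat ages and incidence, and an assumed lag; no actual start dates are in the documents.

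Three stronger readings are not supported:
- That every primary result is exposed. The gender interaction compares girls with boys over the same window, and the coverage outcomes come from surveys, so both are largely unaffected.
- That a safety signal of the targeted size could be hidden or manufactured. The shifts are small against 5.66 and 2.03.
- That any gap in surveillance biases the same way. The direction reverses at about month 23.

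This is an inexpensive improvement to the stated method, chiefly protecting the mortality ratio and then the severe malaria ratio. It is not a demonstrated error in the results.

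**What to change.** In SAP 20, prespecify one analysis start month per country: the first month in which all its clusters and sentinel hospitals are reporting. Exclude earlier events and person-time in both arms, for rate ratios and rate differences alike. This removes start-date bias fully. The cost is some early events, nearly all in group B; if the common month were month 3, that is about 11% of group B time to month 46 and 0.05% of A2.

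As a sensitivity analysis that also covers later gaps, keep the Table 10 T_B/T_A term, computed from the Annex 1 populations over the months each cluster was under surveillance (for hospital outcomes, the months its hospitals were reporting). This does not replace the common start: because incidence varies with age, it leaves about 1-2% for mortality (for example 1.133/1.120 = 1.01 at 3 months, Malawi A2).

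Tabulate surveillance start dates by arm, and reconcile SAP 2 with SAP 6, Protocol 10.3 and Protocol 6 on when surveillance opens. The work is SAP wording and a few lines of code using populations and reporting dates that the plan already collects. Fix the rule before results by arm are seen, since choosing the window afterwards could move the mortality estimate by as much as the expected effect.

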## 9.5 Study size

Planning was based on the assumption that 4,000 children would be born per cluster per year, with 30 months of vaccination and a total surveillance period of 46 months, each cluster contributing 23,750 person years at risk (pyar) if all children survive. If 1% of children die in their first month of life, and 0.08% die every month after the first month, infant mortality would be 18.7 per 1000, mortality (based on estimates of rates for the 5 to 36 months age group) would be 22.2 per 1000, and the average time at risk per cluster would be 23,134 years.

Table 3 shows how this generic approach compares with the expected mortality between 6 and 36 months of age, based on infant and child mortality data in 2015 from the World Bank. The expected mortality between 6 and 36 months of age was estimated as follows: mortality between age 6 to 11 months was assumed to be 50% higher than the mortality during age 1 year, and between age 1 and 4 years the mortality decreases with age as follows: 35% in year 1, 27% in year 2, 20% in year 3 and 18% in year 4. It is assumed that mortality rates in areas with high malaria endemicity are 50% higher than the estimates from the World Bank data.

Table 3: Infant and under five mortality estimates 2015 from World Bank Data, and expected mortality 6m to 36m in high endemic areas in selected countries.

Country	Infant Mortality (per 1000)	Under Five Mortality (per 1000)	Mortality 6m to 36m In high malaria endemic areas (per 1000)
Ghana	43	62	25.2
Kenya	36	49	17.2
Malawi	43	64	27.8

The mortality rate can be estimated from mortality risk as  $-\log_e(1-\text{risk})/\text{time}$ , where risk is the probability of dying during the time of follow-up, assuming an exponential distribution. A mortality risk of 25 per 1,000 equates to a rate, over 2.5 years, of 10.12712 per 1,000 pyar. A mortality risk of 21 per 1,000 equates to a rate, over 2.5 years, of 8.489455 per 1,000 pyar.

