Based on a minimum mortality rate of 8.5 per 1000 pyar, 23 areas each in the evaluation and comparator areas, each with an annual birth cohort of approximately 4,000 subjects, would have 80% power to detect, at the 5% significance level, a decrease of at least 10% in overall mortality in each country. This compares with the modelled estimate of an 18% (range 6-29%) reduction in malaria-specific mortality in children under 5 years, assuming 72% coverage of a 4 dose regimen delivered at 6, 7.5, 9 and 27 months of age. The sample size was obtained after applying the formula from Hayes and Bennett with an intra-class correlation of (k) 0.1. The design effect is

3.01. The total number of areas per country is expected to range from 46-60 and will be presented as part of country-specific sample size calculations in country-specific protocols.

Figure 4 presents a sensitivity analysis showing how the coefficient of variation influences the required number of clusters.

Figure 4: Sensitivity analysis illustrating effect of changing mortality rate and inter-cluster coefficient of variation on number of areas required to detect a 10% reduction in mortality

[figure not shown]

Table 4 shows the reduction in mortality that can be detected at a 5% significance level if the number of areas and the population remain constant but the parameters of baseline mortality and intra-class correlation ( $k$ ) change.

Table 4: Sensitivity analysis of the sample size. Decrease in mortality that can be detected at the 5% significance level with a power of 80% by baseline mortality and coefficient of variation of the mortality between areas assuming 30 areas with an annual birth cohort of 4,000

Mortality risk per 1000 in non-implementing clusters	Coefficient of variation (K)	Detectable decrease in mortality
25	0.10	10.0%
25	0.15	12.6%
25	0.20	15.5%
25	0.30	21.3%
20	0.10	10.6%
15	0.10	11.5%
10	0.10	13.2%
5	0.10	17.3%

Based on simulations, a trial with these characteristics is estimated to have approximately 80% power to detect an interaction between gender and treatment of 1.15 (i.e an increased risk of mortality in girls of 1.035). This compares favourably with the 1.9-fold increase in risk among girls receiving RTS,S/AS01 in the phase 3 trial Mal-055.

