### 10.10 Study size

Assuming a meningitis rate of 0.040% cases per year, a study with 12 areas each in the evaluation and comparator areas, and an annual birth cohort of 4,000 children in each of the evaluation and comparator areas, would have 80% power, across the three countries, to detect a 2.6-fold increase in risk. This sample size was obtained using the formula from Hayes and Bennet with an intra-class correlation (K) of 0.4. This value of K means that the observed rate of meningitis may range from approximately 1/12,500 to 1/1,390 with a mean rate on of 1 /2500. In the Phase 3 trial there was 1 case from 2974 subjects (0.035%) in the control area and a relative risk of 8 to 10, depending on the follow-up.

The same sample size would provide 80% power to detect a 1.7-fold increase in the risk of cerebral malaria, assuming a baseline rate of 0.20% and an intra-class correlation (K) of 0.3. Cerebral malaria is expected to be more common than meningitis. In the Phase 3 trial, there were 6 cases from 2974 subjects (0.06%) in the control arm and a relative risk of about 2.

For the evaluation described in this protocol, approximately 360,000 children per year will be eligible for vaccination with RTS,S/AS01 in the three countries, with a subset of 48,000 per year within the population catchment areas of the sentinel hospitals (Sentinel Hospital level). Table 7 shows the empirical power to detect at least a given number of events according to the true risk and the population size and assuming 90% vaccine coverage. At the sentinel hospital level there would be more than 80% power to detect 1 or more occurrences of a rare event if the true risk is 1 per 10,000 subjects. There is more than 80% power to detect one or more occurrences of rare events in the whole MVIP if the risk is 1/100,000. The power to detect rare events of 1/1,000,000 is low even across the MVIP. The empirical power was estimated using Monte Carlo simulations of 100,000 trials with the given sample size and true probability level.

Table 7: Empirical power to detect rare events

Risk	Observed events				
	≥1	≥2	≥3	≥4	≥5
Sentinel Hospitals (Approximately 108,833 children vaccinated)					
1/10,000	100%	100%	100%	99%	98%
1/100,000	66%	29%	10%	2%	1%
1/1,000,000	10%	1%	0%	0%	0%
ALL MVPE areas (Approximately 816,000 children vaccinated)					
1/10,000	100%	100%	100%	100%	100%
1/100,000	100%	100%	99%	96%	91%
1/1,000,000	56%	20%	5%	1%	0%

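### SAP section 2 states 90% power where the protocol derives 80%; protocol 9.5 mixes two person-time bases; and the death counts in SAP Table 5 row (a) are too low for the printed rate ratio of 0.93

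*SAP*

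**What the plan says.** **Mortality.** SAP section 2 states that "it was powered to detect a reduction in all-cause mortality in each country in RTS,S clusters of 10% or more (with 90% power". Protocol 9.5 states that 23 areas per arm, at 8.5 deaths per 1,000 person-years and k = 0.1, "would have 80% power to detect, at the 5% significance level, a decrease of at least 10% in overall mortality in each country". Two paragraphs earlier it gives the person-time behind this: "the average time at risk per cluster would be 23,134 years". Protocol Table 4 also works at 80% power, for "mortality between areas assuming 30 areas with an annual birth cohort of 4,000"; its first row gives a detectable decrease of 10.0% at a risk of 25 per 1,000 and k = 0.10. SAP section 19 repeats that mortality is powered within each country by month 46.

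**Gender.** Protocol 9.5: "a trial with these characteristics is estimated to have approximately 80% power to detect an interaction between gender and treatment of 1.15". SAP section 2: "to detect an increase in the female:male mortality ratio with 90% power if the ratio is increased by 1.15-fold or more".

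**Meningitis and cerebral malaria.** Protocol 10.10, with 12 areas per arm, "would have 80% power, across the three countries, to detect a 2.6-fold increase in risk", and "The same sample size would provide 80% power to detect a 1.7-fold increase in the risk of cerebral malaria". The protocol abstract gives 90% for both. SAP section 2 gives 90% for meningitis and no power figure for cerebral malaria.

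**SAP Table 5, mortality row (a).** The effect is 0.898 in vaccinated children, 0.92 after coverage and 0.93 after contamination, paired with 24,000 (90%) and 18,000 (80%) deaths. Footnote 5 says these are totals over eligible and non-eligible groups.

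**The concern.** The same effect sizes carry 80% in the sections that derive them and 90% in the summaries. Mortality in each country is a primary objective, so a non-significant country result would be read against the stated power. If that power is overstated, a null result looks like stronger evidence of no benefit than the design can give. Table 5 row (a) has the same consequence for the 7% reduction that its footnote 7 expects.

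**Working it through.** **1. Mortality, protocol text basis.** Inputs from protocol 9.5: λ0 = 0.0085, λ1 = 0.00765, y = 23,134, k = 0.1; 5% taken as two-sided. Hayes–Bennett for rates:

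c = 1 + (zα + zβ)² × [(λ0+λ1)/y + k²(λ0²+λ1²)] / (λ0−λ1)²

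The bracket is 6.98×10⁻⁷ + 1.308×10⁻⁶ = 2.006×10⁻⁶, and (λ0−λ1)² = 7.225×10⁻⁷.
- 80%: 1 + 7.849 × 2.776 = 22.8, so 23 per arm. This reproduces the protocol.
- 90%: 1 + 10.507 × 2.776 = 30.2, so 31 per arm.
- Power at 23 per arm: 80.4%.

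**2. Table 4 basis.** The proportions form with 4,000 per cluster, 30 areas per arm and 80% power gives:

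| Risk per 1,000, k | Printed | Reproduced |
|---|---|---|
| 25, 0.10 | 10.0% | 9.96% |
| 25, 0.15 | 12.6% | 12.5% |
| 25, 0.20 | 15.5% | 15.3% |
| 25, 0.30 | 21.3% | 21.0% |
| 20, 0.10 | 10.6% | 10.6% |
| 15, 0.10 | 11.5% | 11.5% |
| 10, 0.10 | 13.2% | 13.1% |
| 5, 0.10 | 17.3% | 17.1% |

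With 23,134 person-years the first row would be 8.5%. The design effects differ in the same way. The text prints 3.01; 1 + k²yλ0 is 2.97 at 23,134 and 3.02 at 23,750. The Table 4 basis gives about 2.0. On that basis 23 per arm gives 65% (21 per 1,000) to 69% (25 per 1,000); 80% needs 30–33 per arm and 90% needs 40–44.

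**3. Country power for a 10% reduction.** Clusters and birth cohorts come from SAP Table 1, with arms taken as equal (33, 23, 23); risks come from protocol Table 3. The lower end is the Table 4 basis with the country's cohort; the upper end is the text basis with person-time scaled by cohort/4,000.

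| k | Ghana | Kenya | Malawi |
|---|---|---|---|
| 0.05 | 96–99.9% | 85–98% | 93–99.5% |
| 0.10 | 84–94% | 67–82% | 75–86% |
| 0.15 | 64–73% | 48–56% | 52–58% |

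These use the unadjusted two-arm formula, not the SAP's ratio estimator. Under that estimator, Table 5 row (b) needs 17,600 deaths for 90% at 0.90. If that count is pooled and each country supplies a third, power per country is Φ(√(1/3) × 3.2415 − 1.96) ≈ 46%.

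**4. Gender, 1.15-fold.** Scaling Table 5 (1,500 and 2,000 deaths at 1.47) by (ln 1.47 / ln 1.15)² gives about 11,400 deaths for 80% and 15,200 for 90%. One 60-area country has 60 × 23,134 × 0.0085 × 0.95 ≈ 11,200 deaths, about 79% power. Pooled, the SAP Table 1 cohorts (66×3,975 + 46×5,488 + 46×4,820 = 736,518 births a year) scale to about 34,400 deaths, which is ample for 90%.

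**5. Meningitis and cerebral malaria.** With y = 4,000 and 12 per arm: 0.040%, K = 0.4, 2.6-fold gives 81% (90% needs 15.3 per arm); 0.20%, K = 0.3, 1.7-fold gives 80% (90% needs 15.7). The 77 catchment clusters, about 38 per arm, give over 99% at these planning rates. But SAP Annex 4.2, at 0.02 per 1,000, can exclude only a 3.5-fold (90%) or 2.9-fold (80%) increase at month 45.

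**6. Table 5 row (a).** Coverage 74%: 0.74 × 0.898 + 0.26 = 0.9245. Contamination 4%: 0.9245 / (0.04 × 0.898 + 0.96) = 0.9283. The estimator compares eligible:non-eligible event ratios between arms, so under Poisson counts Var(log RR) is the sum of four reciprocal cell counts, at least 16/N. Hence N ≥ 16(zα+zβ)² / (ln RR)².

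| RR | 90% | 80% |
|---|---|---|
| 0.92 | 24,181 | 18,063 |
| 0.9283 | 30,400 | 22,700 |
| 0.93 | 31,900 | 23,800 |
| Printed | 24,000 | 18,000 |

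The printed counts give 82% and 70% at 0.9283, or 80% and 68% at 0.93. Unequal cells or between-cluster variation would only raise the requirement.

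**The case against.** The best defence of 90% is the master design of 60 areas per country. On the 23,134 person-year basis, 30 per arm gives 89.8% at 8.5 per 1,000 and 91.4% at 10.127 per 1,000. That explains where the figure may have come from, but it does not support 90% in each country when Kenya and Malawi have 46 clusters each. Country-specific calculations, to which the protocol defers, may also exist.

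The gender and hospital figures depend on the basis too. With 23,134 person-years per cluster, 12 areas per arm would give 98.6% for meningitis and 95.3% for cerebral malaria, and a simple Poisson check puts gender power near 91% at 23 per arm. For meningitis the SAP agrees with the protocol abstract, so part of the conflict lies inside the protocol. This stands, and it is why these items are only unreconciled.

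Table 5 uses three-country average coverage, and the sentences before the month-46 statement concern pooled analysis, so the mortality counts are probably pooled. The SAP should say so, because section 19 claims power by country.

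On row (a), the match to 0.92 relies on a rounded value; the unrounded pre-contamination ratio of 0.9245 would need about 27,300 and 20,400. The cause is therefore an inference. The shortfall against the printed 0.93 does not depend on it.

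**Conclusion.** The concern holds. For mortality, 90% in each country is unsupported rather than disproved: the protocol's derivation gives 80.4% at 23 per arm, and at k = 0.10 Kenya and Malawi fall short of 90% on either person-time basis, though with k = 0.05 most of the range exceeds 90%. The two bases in protocol 9.5 are incompatible, and moving from one to the other takes 23 per arm from about 80% to 65–69%. The gender, meningitis and cerebral malaria figures need reconciling; true power may be higher or lower than stated. Table 5 row (a) is wrong as printed: the counts are about 21–25% below the minimum, assuming a two-sided 5% test and the SAP's estimator. The effect is on interpretation only, since SAP Annex 3 times the mortality analyses by safety accrual and month 46, not by a death count.

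**What to change.** 1. **Mortality.** In SAP section 2, give the protocol's 80% at 23 areas per arm, or cite the country-specific calculation that yields 90%; align section 19. In protocol 9.5, reconcile the text with Table 4 and state the person-time per cluster each uses. In SAP section 8, say whether the mortality counts and the month-46 statement are pooled or per country. Give any country power as a range over k and person-time basis, under the SAP's ratio estimator.
2. **Gender.** Give approximately 80% as the planning figure and say whether it is per country or pooled, or cite the calculation giving 90%.
3. **Meningitis and cerebral malaria.** Give 80% as the planning figure for 12 areas per arm in the protocol abstract and, for meningitis, in SAP section 2; or recalculate for the 77 catchment clusters at observed incidence.
4. **Table 5 row (a).** Rerun at the post-contamination ratio, or correct the pairing of effect size and counts. Check the month-46 claim of 80% power for an 8% reduction at the same time: 18,000 deaths give 80% at 0.92 but only 68–70% at 0.928–0.93.

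The cost is wording and one table row. Sample, estimator, timing and decisions are unaffected, though some stated power figures may become less favourable.
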